4.7.3 Deaths

The following summaries of patient deaths will be provided:

- All deaths by primary cause of death
- Incidence and cause of deaths within 30 days of the start of treatment

4.7.4 Laboratory Data

Laboratory toxicities will be defined on the basis of local laboratory normal ranges and the NCI CTCAE v4.0. Laboratory test results and normal ranges will be converted from local lab to Standard International units for analysis purposes. For each laboratory parameter, the toxicity grade at baseline and the worst toxicity grade during the treatment period will be summarized by treatment arm.

4.7.5 Vital Signs

No analyses of vital signs or physical-examination findings are planned.

4.8 MISSING DATA

For DFS, data from patients who are lost to follow-up without DFS event will be censored at the date of the last disease assessment. If no post-randomization disease assessment is available, the data will be censored on the randomization date.

For DMFS, data from patients who are lost to follow-up without documented distant melanoma recurrence will be censored at the date of the last disease assessment. The data of the patients without post-randomization disease assessments will be censored on date of randomization.

For OS, data from patients who are lost to follow-up will be analyzed as censored observations on the date the patient was last known to be alive. The data of patients without post-randomization disease assessments will be censored on date of randomization.

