4.6.1.2 Withdrawal from Study

The primary reason for withdrawal from the study should be documented on the appropriate eCRF. If patient is lost to follow-up, the investigator should make every effort to contact the patient by telephone or by sending a registered letter to establish as completely as possible the reason for the withdrawal and survival status. These steps for contacting patients (who prematurely withdraw or who are lost to follow-up) will be documented in the patient informed consent form.

Patients who withdraw their consent to be followed for the primary study endpoint (DFS) will be asked to continue follow-up for OS until *end of study* (see Section 3.2), as well as for new primary malignancies until *end of study* (see Section 3.2). Patients will not be followed for any reason after full consent, for DFS, OS, and new primary malignancies, has been withdrawn. Patients who withdraw from the study will not be replaced.

An excessive rate of withdrawals can potentially render the study non-interpretable; therefore, unnecessary withdrawal of patients should be avoided. Should a patient decide to withdraw, all efforts will be made to complete and report the observations prior to withdrawal as thoroughly as possible.

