4.4.2 Secondary Efficacy Endpoints

4.4.2.1 Distant Metastasis–Free Survival

DMFS is defined as the time from randomization until the date of diagnosis of distant (i.e., non-locoregional) metastasis or death from any cause. For patients without a DMFS event at the time of data cutoff, the data will be censored at the date of the last disease assessment. If no post-randomization disease assessment is available, the observation will be censored on the randomization date.

DMFS will be analyzed at the time of the final DFS analysis in each cohort. The analysis methods to be employed for DMFS are the same as those described for the primary endpoint of DFS.

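### The lost-to-follow-up rule for DMFS in SAP 4.8 leaves out death, so read literally it can censor a known death that SAP 4.4.2.1 counts as an event

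*SAP*

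**What the plan says.** Four statements in the SAP bear on this.

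- **Endpoint (SAP 4.4.2.1).** "DMFS is defined as the time from randomization until the date of diagnosis of distant (i.e., non-locoregional) metastasis or death from any cause".
- **Censoring at cutoff (SAP 4.4.2.1).** "For patients without a DMFS event at the time of data cutoff, the data will be censored" at the last disease assessment. A patient who has died has had a DMFS event, so this rule does not censor that patient.
- **Loss to follow-up, DMFS (SAP 4.8), with censoring at the last assessment.** "For DMFS, data from patients who are lost to follow-up without documented distant melanoma recurrence will be censored at the date of the last disease". Only one of the two DMFS components, distant recurrence, appears in the condition.
- **Loss to follow-up, DFS (SAP 4.8).** "data from patients who are lost to follow-up without DFS event will be censored at the date of the last disease assessment". Here the condition is the whole composite, death included.

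SAP 4.4.2.1 also ties the two endpoints together: "The analysis methods to be employed for DMFS are the same as those described for the primary endpoint of DFS".

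The plan collects deaths after disease follow-up has ended. Protocol 4.6.1.2 says: "Patients who withdraw their consent to be followed for the primary study endpoint (DFS) will be asked to continue follow-up for OS". The same section has sites try to establish survival status for patients who are lost. Protocol 4.5.2.6 keeps patients who leave post-treatment follow-up in survival follow-up. Protocol 4.5.2.7 allows public records to be used for survival status after withdrawal from study follow-up.

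**The concern.** The SAP has two censoring rules for DMFS and does not say which prevails. They agree for most patients. They part for a patient who is lost to disease follow-up, has no documented distant recurrence, and is known to have died before the cutoff. Under 4.4.2.1 that death is an event on its date. Under the literal 4.8 condition the patient can be censored at the last disease assessment. The DFS sentence in 4.8 would keep the same death as a DFS event.

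DMFS is the first secondary test in each cohort and gates OS (SAP 4.4.2.4), so its event rule should be unambiguous. If disease follow-up were lost more often in one arm, the choice of rule could also affect the comparison. The protocol's definition does not settle the matter: it matches SAP 4.4.2.1, the conflict lies within the SAP, and SAP Section 1 gives the SAP precedence for registration purposes.

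**Working it through.** **1. The two rules applied to the same patient**

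| Patient | SAP 4.4.2.1 | SAP 4.8, read literally |
|---|---|---|
| Lost, no distant recurrence, not known to have died | Censored at last disease assessment | Censored at last disease assessment |
| Distant recurrence documented before loss | Event | Not covered, so event |
| Lost, no distant recurrence, death later known | Event at death | Condition met, so censored |

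Only the third row differs.

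**2. Can the third row occur?** SAP 2.3 assumes 5% annual loss for DFS. The note to SAP Table 2 assumes 1% annual dropout for OS. The gap implies patients whose disease follow-up ends while their survival status is still known, and the protocol sections listed above provide for this.

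**3. Planning inputs.** There is no DMFS event count, power or hazard ratio in the documents to reproduce. The DFS and OS planning figures that feed the size estimate were checked with Schoenfeld's formula at two-sided 0.05 and 1:1 allocation: power = Φ(|ln HR| × √d / 2 − 1.96).

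| Analysis | Events d | HR | Computed | Stated |
|---|---|---|---|---|
| DFS, Cohort 1 | 120 | 0.60 | 79.9% | 80% |
| DFS, Cohort 2 | 105 | 0.58 | 79.7% | 80% |
| OS, Cohort 1 | 107 | 0.70 | 45.4% | 0.45 |
| OS, Cohort 2 | 118 | 0.70 | 49.1% | 0.49 |

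All four agree.

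**4. Size of the affected group.** Two simulations used the planned medians: DFS 24 v 40 and 7.7 v 13.3 months, OS 61 v 87.1 and 24.2 v 34.6 months, for Cohorts 1 and 2. Both assumed exponential times and uniform accrual. Monthly loss hazards are −ln(0.95)/12 = 0.0043 for disease follow-up and −ln(0.99)/12 = 0.0008 for survival.

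- *Simple model.* Accrual over 43 months (Cohort 1) and 40 months (Cohort 2), cutoff at Month 50, with the OS hazard restarting at loss. Cohort 1: about 24 patients lost before a DFS event, of whom about 4 (95% range 1 to 8) have a later known death. Cohort 2: about 9 lost, of whom about 3 (0 to 7) have a later known death. These are upper-end figures. Every DFS loss is treated as lost under 4.8, and the full OS hazard applies at once to patients who have not yet recurred. The model also yields 128 and 138 DFS events against planned targets of 120 and 105, so it carries more follow-up than the event targets imply.
- *Recurrence-driven model.* Assumes 40% to 70% of first recurrences are distant, with survival after distant metastasis calibrated to the OS medians. At Month 50, Cohort 1 has 1.6 to 1.7 affected deaths among 79 to 105 DMFS events, at most 1.7/79 = 2.2%. Cohort 2 has 2.2 to 2.3 among 115 to 127, at most 2.3/115 = 2.0%. At Month 56 the count is about 3 per cohort. The Cox hazard ratio differs between the two rules by less than 0.005.

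**The case against.** The strongest case on the other side is that 4.8 is headed Missing Data and concerns patients whose outcome is unknown. A recorded death is not missing, and a patient known to have died would not normally be classed as lost. The OS sentence in 4.8 also lacks an exception for death. Read with the same literalness, it would censor known deaths in the OS analysis, which nobody intends. Where the SAP does mean to censor a death after missed assessments it says so, and only in a DFS sensitivity analysis (SAP 4.4.1). An analyst who follows 4.4.2.1 gets one clear answer.

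Much of this stands. It is probably what the authors meant, and it makes this a drafting inconsistency rather than a chosen rule. It does not remove the inconsistency. The OS sentence censors at the date last known alive, which presupposes no known death. The DMFS sentence instead names the outcome that must be undocumented, and names only one of the two. Loss is also endpoint-specific in this plan, since SAP 2.3 speaks of loss for DFS at a rate different from OS dropout. A patient can therefore be lost to disease assessment with a known date of death.

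A further fair point is that the passage quoted from Protocol 4.6.1.2 concerns withdrawal of consent for DFS follow-up. The protocol distinguishes withdrawal from loss, so not every such patient falls under 4.8. That reduces the count without making it zero.

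**Conclusion.** The point holds as a wording conflict in a secondary endpoint. The DMFS condition in SAP 4.8 is narrower than the DMFS definition and out of line with the parallel DFS sentence. Read literally, it can censor a known death that 4.4.2.1 counts. It affects only patients lost to disease follow-up whose death is later known: roughly 2 to 4 per cohort at the planned loss rates, with a negligible change in hazard ratio. Those counts rest on exponential times, uniform accrual, a Month 50 cutoff and, in one model, an assumed share of distant first recurrences.

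A reader might infer more, in three ways that the documents do not support.

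- *That the SAP directs later deaths to stay censored, or censors deaths generally.* SAP 4.8 does not say so. This follows only from taking its condition literally, and the condition covers lost patients only.
- *That the treatment estimate is materially at risk.* Differences of 0.01 to 0.04 in hazard ratio, with 2 to 7 affected deaths, appear only if annual disease-follow-up loss is assumed to be 10% to 15% on vemurafenib against 5% on placebo. No such difference is planned or reported in the documents.
- *That a confirmatory DMFS or OS result turned on it.* SAP 4.4.2.4 tests DMFS only in a cohort whose DFS is significant. The rationale for protocol amendment version 10 reports that Cohort 2, tested first, did not meet DFS, so the DMFS step was not formally reached. What depends on the rule is the descriptive DMFS estimate.

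Primary DFS, alpha and sample size are unaffected.

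**What to change.** In the DMFS sentence of SAP 4.8, replace the condition about documented distant recurrence with *without a DMFS event (neither distant metastasis nor death from any cause)*. A death learned of after loss of disease follow-up then counts as a DMFS event on its date, as in 4.4.2.1, and the sentence matches the DFS wording above it. If DMFS has already been programmed, record which rule was applied.

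The cost is one phrase in the SAP. A DMFS counterpart to the DFS sensitivity analysis that censors deaths after two or more missed assessments would be optional and is not part of this correction.

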4.9 INTERIM ANALYSES

An independent DSMB will monitor the safety of patients and will meet periodically to review summaries of selected safety data prepared by the independent Data Coordinating Center. The detailed interim safety analysis plan and the role and responsibilities of the DSMB members are described in the interim analysis plan and separate charter for the DSMB, respectively.

Interim analyses of OS will be performed by the Sponsor (see Section [4.4.2.2](#)).

4.9.1 Efficacy

No interim analyses of the primary endpoint, DFS, will be performed.

Two OS analyses (one interim analysis and one final analysis) are planned for each cohort. The OS interim analysis will be performed at the time of the final DFS analysis for both cohorts. The final OS analysis for Cohorts 1 and 2 will be performed after the occurrence of approximately 107 and 118 deaths, respectively (projected to occur at approximately Month 72 in each cohort) or at Month 72, whichever occurs first.

The Lan-DeMets implementation ([Lan and Demets 1983](#)) of the O'Brien-Fleming use function will be used to control the overall Type I error for the OS comparison in each cohort at a two-sided 0.05 significance level. [Table 2](#) summarizes the assumptions and characteristics of the analyses for OS.

Table 2 Assumptions and Characteristics for Overall Survival Analyses by Cohort

	Cohort 1 n=300	Cohort 2 n=175
HR targeted	0.70	0.70
Targeted median (control)	61 months	24.2 months
Targeted median (vemurafenib)	87.1 months	34.6 months
Interim OS (to be performed at time of final DFS analysis)		
Projected number of events (% of final events)	64 (60%)	59 (50%)
Final OS		
Number of events (% of final events)	107 (100%)	118 (100%)
Estimated cutoff date ^a	72 months after FPI	72 months after FPI
α level (two sided)	0.05	0.05
Power	0.45	0.49

DFS = disease-free survival; FPI = first patient in; HR = hazard ratio; OS = overall survival.

Note: 1% annual dropout rate is anticipated for OS analyses.

^a Estimated data cutoff time from study enrollment date.

25. Have you had difficulty remembering things?	1	2	3	4
26. Has your physical condition or medical treatment interfered with your family life?	1	2	3	4
27. Has your physical condition or medical treatment interfered with your social activities?	1	2	3	4
28. Has your physical condition or medical treatment caused you financial difficulties?	1	2	3	4

For the following questions please circle the number between 1 and 7 that best applies to you

29. How would you rate your overall health during the past week?

1 2 3 4 5 6 7

Very poor

Excellent

30. How would you rate your overall quality of life during the past week?

1 2 3 4 5 6 7

Very poor

Excellent
